### **5.3 Lifestyle Considerations**

#### **5.3.1 Contraception**

- 1 Women must be 1 year post-menopausal, surgically sterile or must agree to using enhanced contraceptive measures for the duration of the study and for 5 months after the last dose of study drug, with all male sexual partners. Highly effective methods of contraception must be used, which include having a vasectomised partner, sexual abstinence (defined as refraining from heterosexual intercourse during the study and for 5 months after the last dose of study drug. The reliability of sexual abstinence needs to be evaluated by the Investigator, in relation to the duration of the study and the preferred/usual lifestyle of the subject), or one of the following: hormonal contraceptives which inhibit ovulation (oral, injectable, transdermal, intravaginal or implants), Intrauterine Device (IUD), Intrauterine Hormone-releasing System (IUS) (e.g., Mirena), or bilateral tubal occlusion.
- 2 Men must use a condom (with spermicide) during the study, and for 5 months after the last dose of study drug, with all sexual partners.
- 3 Men must not donate sperm for 5 months after the last dose of study drug.

#### **5.3.2 Meals and Dietary Restrictions**

Patients must fast (water to drink only) from at least 2 hours prior to taking a dose to at least 1-hour post-dose for all doses. Patients should abstain from eating large amounts of grapefruit and Seville oranges (and other products containing these fruits e.g. grapefruit juice or marmalade) during the study (e.g., no more than a small glass of grapefruit juice (120 mL) or half a grapefruit or 1-2 teaspoons (15g) of Seville orange marmalade daily).

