## Assessment of potential for other risks

### Potential for Drug-Drug Interactions with CYP3A4 inhibitors

RXC004 has not shown the potential to induce or inhibit CYP enzymes or transporters at the dose to be investigated in this study but it is exclusively metabolised by CYP3A4 and as such has the potential to be a victim for drug-drug interactions with potent CYP inhibitors (which could increase levels of RXC004, leading to a higher risk of adverse events). As such, strong and moderate CYP3A4 inhibitors are contra indicated in this protocol (see Appendix E). Patients with colorectal cancers commonly require co-medication with analgesics, antibiotics, anti-emetics and anti-depressant or anxiolytic drugs, some of which are CYP3A4 inhibitors. The table in Appendix E highlights the CYP3A4 inhibitors which are also likely to be commonly used in colorectal cancer patients. These drugs should be avoided, and alternatives used wherever possible. If it is not possible to use an alternative (e.g. if a specific antibiotic or anti-fungal treatment is needed), RXC004 should be interrupted.

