#### **5.3.3 Concomitant treatments**

##### **5.3.3.1 Prohibited medications**

The following concomitant medication is prohibited without approval from the Sponsor Physician;

- 1 The use of any natural/herbal products or other 'folk remedies'.

- 2 No other chemotherapy, hormonal therapy (contraception and hormone replacement therapy is acceptable), or other investigational product is permitted other than the study treatments.
- 3 Live or live-attenuated virus and bacterial vaccines should not be administered, e.g. yellow fever, measles, influenza nasal spray, COVID-19, rubella, mumps, typhoid, mycobacterium tuberculosis (BCG), Yersinia pestis (EV) within 4 weeks of starting study treatment, whilst the patient is receiving study medication and for 30 days following discontinuation of study treatment. Patients who require COVID-19 vaccination whilst on study should receive a non-live vaccine (e.g. one based on mRNA or fully inactivated/genetically modified viruses incapable of replication).
- 4 The use of some CYP3A4 inhibitors and inducers should be restricted prior to first dose of study treatment and throughout the study treatment, as RXC004 is observed to be exclusively metabolised by CYP3A4. For a list of prohibited CYP3A4 inhibitors and inducers and the required washout periods, please refer to Appendix E.
- 5 Drugs that are immunosuppressive or may cause secondary osteoporosis should not be administered (e.g. corticosteroids, pioglitazone or rosiglitazone).

The following exceptions are allowed:

- Use of immunosuppressive medication for the management of nivolumab-related AEs (as per Appendix G) or colitis events (as per Appendix J). Steroids required for the management of RXC004 or nivolumab related AEs, should be tapered to doses  $\leq$  10 mg/day prednisone equivalent, before re-starting study treatment.
- Use of topical, inhaled or intranasal corticosteroids
- Systemic steroids at doses  $\leq$  10 mg/day prednisone equivalent

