## Appendix E Prohibited CYP3A4 Inhibitors, and Inducers

CYP3A4 Inhibitors	CYP3A4 Inducers

CYP3A4 Inhibitors
 
[Bold text denotes commonly used co-medications in patients with colorectal cancer]
	
CYP3A4 Inducers
 
[None of these drugs are commonly used co-medications in patients with colorectal cancer]

Strong CYP3A4 Inhibitors
 
Concomitant use of these drugs has the potential to increase the exposure of RXC004 over 5-fold
 
These agents must not be given within 14 days of first dose of study treatment
 
boceprevir, cobicistat, danoprevir and ritonavir, elvitegravir and ritonavir, grapefruit juice, indinavir and ritonavir, itraconazole, ketoconazole, lopinavir and ritonavir, paritaprevir and ritonavir and (ombitasvir and/or dasabuvir), posaconazole, ritonavir, saquinavir and ritonavir, telaprevir, tipranavir and ritonavir, troleandomycin, voriconazole, clarithromycin, idelalisib, nefazodone, neflifinavir,
	
Strong CYP3A4 Inducers
 
Concomitant use of these drugs has the potential to decrease the exposure of RXC004 by over 80%
 
aptalutamide, carbamazepine, enzalutamide, mitotane, phenytoin, rifampin, St. John's wort
 
These agents must not be given within 14 days of first dose of study treatment

Moderate CYP3A4 Inhibitors
 
Concomitant use of these drugs has the potential to increase the exposure of RXC004 by 2-5-fold
 
A washout period of 14 days is recommended and a minimum washout period of 5 half-lives (See SPC or USPI) is required before first dose of study treatment.
 
aprepitant, ciprofloxacin, conivaptan, crizotinib, cyclosporine, diltiazem, dronedarone, erythromycin, fluconazole, fluvoxamine, imatinib, tofisopam, verapamil lansoprazole
	
Moderate CYP3A4 Inducers
 
Concomitant use of these drugs has the potential to decrease the exposure of RXC004 by 60-80%
 
A washout period of 14 days is recommended and a minimum washout period of 5 half-lives (See SPC or USPI) is required before first dose of study treatment
 
bosentan, efavirenz, etravirine, phenobarbital, primidone

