
Weak CYP3A4 Inhibitors
 
These are not prohibited but should be used with caution as they may increase the exposure of RXC004 by 1.25 -2- fold
 
chlorzoxazone, cilostazol, cimetidine, clotrimazole, fosaprepitant, istradefylline, ivacaftor, lomitapide, ranitidine, ranolazine, ticagrelor, omeprazole
	
Weak CYP3A4 Inducers
 
These drugs are not prohibited- they have the potential to decrease the exposure of RXC004 by 20-50% which is within the scope of the dose reduction allowances

[figure not shown]
	armodafinil, modafinil, rufinamide
--	------------------------------------

For updated information, please refer to <https://www.fda.gov/drugs/drug-interactions-labeling/drug-development-and-drug-interactions-table-substrates-inhibitors-and-inducers>

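### Section 5.3.2 of the protocol accepts up to 120 mL of grapefruit juice a day, while Appendix E lists grapefruit juice, with no volume limit, among the prohibited strong CYP3A4 inhibitors

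*Protocol*

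**What the plan says.** **Section 5.3.2 (Meals and Dietary Restrictions)** has two rules. The first is fasting: "Patients must fast (water to drink only) from at least 2 hours prior to taking a dose to at least 1-hour post-dose". The second asks patients to avoid large amounts of grapefruit, Seville oranges and products made from them during the study. The example of an acceptable daily limit is "no more than a small glass of grapefruit juice (120 mL) or half a grapefruit", or a small quantity of Seville orange marmalade.

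**Appendix E** is titled as a list of prohibited CYP3A4 inhibitors and inducers. Its strong-inhibitor cell contains the run "elvitegravir and ritonavir, grapefruit juice, indinavir and ritonavir". The timing sentence in that cell is "These agents must not be given within 14 days of first dose of study treatment". The weak-inhibitor cell has a different instruction, "These are not prohibited but should be used with caution", and grapefruit juice is not in it.

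**Section 5.3.3.1 (Prohibited medications), item 4**, treats certain agents that inhibit or induce this enzyme as "restricted prior to first dose of study treatment and throughout the study treatment, as RXC004 is observed to be exclusively metabolised by CYP3A4". It then sends the reader to the appendix: "For a list of prohibited CYP3A4 inhibitors and inducers and the required washout periods, please refer to Appendix E". The items in that section are prohibited unless the Sponsor Physician approves them.

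**Section 2.3.1.2**, under drug-drug interactions, says that "strong and moderate CYP3A4 inhibitors are contra indicated in this protocol (see Appendix E").

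**The concern.** Two operative parts of the protocol give different answers about one named item. A patient who drinks a small glass of juice each day stays within Section 5.3.2 and takes something that Appendix E lists as prohibited. A site cannot tell from the text whether that is acceptable, needs the Sponsor Physician's agreement, or is a deviation.

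The rule exists for safety. The protocol describes CYP3A4 as the only metabolic route for RXC004, and Section 2.3.1.2 gives higher drug levels and more adverse events as the reason for excluding potent inhibitors. An instruction of that kind should read the same wherever a site looks it up.

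**Working it through.** There is no figure in the plan to reproduce. The check is a comparison of the texts.

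| Question | Section 5.3.2 | Appendix E, with Sections 5.3.3.1 and 2.3.1.2 |
|---|---|---|
| Is grapefruit juice named? | Yes | Yes, in the strong-inhibitor cell |
| Amount accepted | Up to 120 mL daily | None stated; the entry carries no volume or strength qualifier |
| Before first dose | No separate rule | Not within 14 days of first dose |
| During treatment | The 120 mL ceiling applies throughout the study | Restricted throughout treatment (5.3.3.1); contraindicated (2.3.1.2) |
| Approval step | None | Sponsor Physician may approve (5.3.3.1) |

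**Step 1: before first dose.** The conflict is direct for any part of the 14 days in which a patient follows Section 5.3.2. Appendix E says strong inhibitors must not be given, and it counts juice as one.

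**Step 2: during treatment.** Appendix E's timing sentence does not extend past first dose, so it does not by itself ban juice on treatment. The restriction is assembled from three places: the word prohibited in the appendix title, the contraindication in Section 2.3.1.2, and the restriction throughout treatment in Section 5.3.3.1, which uses Appendix E as its list.

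**Step 3: does the approval clause reconcile them?** No. Section 5.3.3.1 allows exceptions case by case. Section 5.3.2 accepts 120 mL for everyone without asking.

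**Step 4: does the fasting rule reconcile them?** No. It keeps juice away from the dose from 2 hours before to 1 hour after, but Appendix E makes no exception for time of day.

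**Step 5: could juice sit in a tolerated class?** Appendix E has one, the weak inhibitors, and juice is not placed there.

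**Step 6: scope.** Appendix E names juice only, so half a grapefruit or a little marmalade under Section 5.3.2 does not contradict it. Section 5.3.2's silence on a washout is not a fault either, because Appendix E supplies one.

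**Step 7: room for the 14 days.** Screening runs from Day -28 to Day -1 (Tables 1 and 2). A patient who stops juice at the start of that window has 28 - 14 = 14 days left after the juice-free period.

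**The case against.** The best opposing case is that Section 5.3.2 is the specific rule on diet and should govern. Appendix E is reached through a section on medications and speaks of drugs and agents that are given. Section 5.3.3.1 says only that some inhibitors should be restricted, and it allows approved exceptions. The appendix may have copied a general list in which high-strength juice was meant.

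Part of this stands. The on-treatment restriction is assembled from several places and is softer than an outright ban. But if Section 5.3.2 alone governed, the named juice entry in Appendix E would have no effect, and nothing in the text limits that entry to a strength or volume. Neither section refers to the other on juice or says which prevails.

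A second objection is that no safety cost is shown. That is correct. A reader might infer that a daily small glass raises RXC004 exposure over 5-fold, because Appendix E gives that potential for strong inhibitors. That is a label for the class, not an estimate for 120 mL. A reader might also infer that juice could take a patient on 2 mg, a tolerated dose, to the exposures seen at 3 mg, which was not tolerated. Without an exposure figure for 120 mL, the documents support neither step. The protocol also allows weak inhibitors, with caution, at a stated 1.25- to 2-fold increase, and nothing shows that a capped amount of juice exceeds that.

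**Conclusion.** The inconsistency is real and minor. Section 5.3.2 accepts up to 120 mL of grapefruit juice daily without approval, while Appendix E lists juice among prohibited strong inhibitors with no volume limit. The mismatch in wording is certain. Its clinical consequence is unknown: the documents give neither the effect of 120 mL on RXC004 exposure nor the number of patients who drink it, and they show no harm.

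The conclusion on the treatment period assumes that Sections 2.3.1.2 and 5.3.3.1 extend the Appendix E list beyond first dose, as their wording indicates. What patients are actually told is not visible here. No endpoint, sample size or decision rule in the protocol or SAP is affected.

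**What to change.** Delete only the juice allowance from Section 5.3.2 and keep everything else: the limit on large amounts of grapefruit and Seville oranges, the clause covering other products made from these fruits (with marmalade as its example), and the daily limits of half a grapefruit or 15 g of Seville orange marmalade. Removing the other-products clause would loosen the present rule. Then add a sentence such as: *Grapefruit juice must be avoided from 14 days before the first dose until RXC004 discontinuation (see Appendix E).*

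If the sponsor holds data supporting 120 mL, the better change is the reverse: qualify the Appendix E entry by volume and cross-refer to Section 5.3.2. Either way, one rule should appear in both places, and any patient materials that repeat the allowance should be aligned. Extending the ban to whole grapefruit or Seville oranges is optional and goes beyond removing the conflict.

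The cost is a wording amendment with the usual approvals and, under the first option, the loss of a small daily glass of juice. A patient who has recently drunk juice and is otherwise ready to start may have a short wait within the 28-day screening window. No visits, tests or data collection are added.

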#### **5.3.3 Concomitant treatments**

##### **5.3.3.1 Prohibited medications**

The following concomitant medication is prohibited without approval from the Sponsor Physician;

- 1 The use of any natural/herbal products or other 'folk remedies'.

- 2 No other chemotherapy, hormonal therapy (contraception and hormone replacement therapy is acceptable), or other investigational product is permitted other than the study treatments.
- 3 Live or live-attenuated virus and bacterial vaccines should not be administered, e.g. yellow fever, measles, influenza nasal spray, COVID-19, rubella, mumps, typhoid, mycobacterium tuberculosis (BCG), Yersinia pestis (EV) within 4 weeks of starting study treatment, whilst the patient is receiving study medication and for 30 days following discontinuation of study treatment. Patients who require COVID-19 vaccination whilst on study should receive a non-live vaccine (e.g. one based on mRNA or fully inactivated/genetically modified viruses incapable of replication).
- 4 The use of some CYP3A4 inhibitors and inducers should be restricted prior to first dose of study treatment and throughout the study treatment, as RXC004 is observed to be exclusively metabolised by CYP3A4. For a list of prohibited CYP3A4 inhibitors and inducers and the required washout periods, please refer to Appendix E.
- 5 Drugs that are immunosuppressive or may cause secondary osteoporosis should not be administered (e.g. corticosteroids, pioglitazone or rosiglitazone).

The following exceptions are allowed:

- Use of immunosuppressive medication for the management of nivolumab-related AEs (as per Appendix G) or colitis events (as per Appendix J). Steroids required for the management of RXC004 or nivolumab related AEs, should be tapered to doses  $\leq$  10 mg/day prednisone equivalent, before re-starting study treatment.
- Use of topical, inhaled or intranasal corticosteroids
- Systemic steroids at doses  $\leq$  10 mg/day prednisone equivalent

### 5.3.3.2 COVID-19 Vaccinations

COVID-19 vaccination is permitted before or during study treatment, with the exception of live-attenuated vaccines and replication-competent vector vaccines, which are prohibited within 4 weeks of starting study treatment and whilst on study treatment.

As COVID-19 vaccines are often prioritised for cancer patients, vaccination prior to the first dose of study treatment is advisable. Where possible, COVID-19 vaccinations should be given at least 72 hours before starting study treatment and study treatment should not commence until any acute adverse effects from vaccination have resolved to at least Grade 1. If this is not possible, investigators should follow their local prescribing information and policies when considering whether a patient on study treatment should receive a COVID-19 vaccination. If COVID-19 vaccination is given during the study (including the screening period), then please ensure that all the relevant information is recorded in the concomitant medication eCRF (i.e vaccine name, manufacturer, date(s) given and dose).

### 5.3.4 Other Lifestyle Considerations

Patients taking RXC004 are advised to avoid exposure to direct sunlight and the use of tanning equipment.

## 5.4 Screen Failures

Screen failures are defined as participants who consent to participate in the clinical study but are not subsequently treated in the study. A minimal set of screen failure information is required to ensure transparent reporting of screen failure participants to meet the Consolidated Standards of Reporting Trials (CONSORT) publishing requirements and to respond to queries from regulatory authorities. Minimal information includes demography, screen failure details, eligibility criteria, and any serious adverse event (SAE).

Individuals who do not meet the Calcium and/or Vitamin D3 laboratory criteria for participation in this study may be retested after starting Calcium/Vitamin D3 supplementation. Repeating laboratory tests within the screening period will not be considered as a rescreen.

## 5.5 Pre-Screening Genetic Testing

All enrolled patients' tumours will be required to have a genetic mutation which is predicted to be loss of function in RNF43, or an RSPO fusion/translocation detectable in **CCI** **CCI** **CCI**. Eligible patients also need to have evidence of MSS status. Eligible subjects will be identified by either a central genetics screening approach or local laboratory assessments.

### 5.5.1 Central Testing

Category	Value
1	1
2	2
3	3
4	4
5	5
6	6
7	7
8	8
9	9
10	10
11	11
12	12
13	13
14	14
15	15

CCI [REDACTED]

CCI [REDACTED]

CCI [REDACTED]

CCI [REDACTED]

CCI [REDACTED]

Data from central genetic screening will be shared with investigators to aid future treatment decisions.

CCI [REDACTED]

CCI [REDACTED]

CCI [REDACTED]

CCI [REDACTED]

### 5.5.2 Local Testing

Patients with predicted loss of function RNF43 mutations or RSPO fusions from other local testing will also be eligible to enter the study, provided that the assay used for testing has adequate analytical validation for this purpose (i.e. fully CCI [REDACTED] for the purpose of investigating RNF43 mutations or RSPO fusions; partially CCI [REDACTED] for their analytical performance or having achieved a minimum validation specification of >90% for Analytical Sensitivity / PPA and >95% for Analytical Specificity / NPA for the detection of the aberrations in the genes of interest and performed in an ISO accredited, CLIA or CAP accredited lab). If aberrations are detected by local tests that are not included in the list in Appendix F, these may be included in the study on discussion with the Sponsor. CCI [REDACTED]

CCI [REDACTED]

CCI [REDACTED]

CCI [REDACTED]

### 5.5.3 MSS/MSI Testing

Tumour samples that test positive for RNF43 mutations or RSPO fusions will also be tested for MSI status at CCI [REDACTED]. The MSI status from CCI [REDACTED] CCI [REDACTED] is not required for eligibility (which will be based on the local standard of care IHC, NGS or PCR test that has been taken at diagnosis to identify patients with Lynch Syndrome or patients with MSI CRC who may be eligible for treatment with a PD-1 inhibitor), but will be used to retrospectively evaluate the concordance between local and central MSI assays.

## 6 STUDY TREATMENT

### 6.1 Study Treatment(s) Administered

#### 6.1.1 Investigational Products

**Table 13** Investigational Products

Treatment	RXC004	Nivolumab	Denosumab
ARM	Arm A and B	Arm B and Arm A combination treatment phase	Arm A and B
Type	Drug	Biologic	Biologic
Dose Formulation	0.5 mg or 1 mg capsules	Ampule	Ampule
Dosage Level(s)	Monotherapy: 2 mg QD Combination therapy: 1.5 mg QD	480 mg q4w	120 mg once every month
Route of Administration	oral	IV infusion	SC injection
Use	Experimental	Experimental	Prophylactic
IMP and NIMP	IMP	IMP	IMP
Sourcing	Provided centrally by the Sponsor	Provided centrally by the Sponsor	Provided centrally by the Sponsor
Packaging and Labelling	RXC004 will be provided in white 50 mL HDPE Duma bottles. Each bottle will be labelled as required per country requirement	Study Intervention will be provided in packets of 240 mg/24 mL vials. Each packet will be labelled as required per country requirement	Study Intervention will be provided in a vial containing 120 mg in 1.7 mL solution  Each vial will be labelled as required per country requirement

HDPE, high-density polyethylene; IMP, investigational medicinal product; IV, intravenous; NIMP, non-investigational medicinal product; QD, once daily; q4w, once every 4 weeks; SC, subcutaneous.

### 6.2 Preparation/Handling/Storage/Accountability of Study Treatments

#### 6.2.1 RXC004

RXC004 will be supplied by Redx as 0.5 and 1.0 mg capsules. A complete description of the chemistry and formulation may be found in the Investigational Medicinal Product Dossier.

The Quality Control Standards and requirements for RXC004 study medication are described in separate release protocols/ Certificate of Analysis.

RXC004 is formulated as two dosage strengths capsules (0.5 mg and 1.0 mg), manufactured by Quay Pharma, [name]. The RXC004 capsules strengths are 0.5, 1.0 mg for oral administration. Stability testing of RXC004 is ongoing. Please refer to the current IMP label for the Expiry Date associated with the current shelf-life of the product.

Patients must fast (water to drink only) for at least 2 hours prior to taking a dose to at least 1-hour post-dose for all doses.

